### **15.3. LABORATORY DATA**

The following laboratory parameters will be analyzed:

**Table 16: Summary of Clinical Laboratory Tests**

Hematology	Chemistry	Urinalysis	Coagulation
Basophils Eosinophils Hematocrit Hemoglobin Lymphocytes Monocytes Neutrophils/ANC Platelets Red blood cells (RBC, Erythrocytes), White blood cells (WBC, Leucocytes)	ALT AST Bilirubin (total and direct) a Albumin Alkaline phosphatase Bicarbonate (HCO 3 ) BUN Urea Calcium Chloride CK Serum CK isoenzymes (CK BB, CK MM, CK MB) Creatinine Glucose LDH Magnesium Potassium Sodium Total protein Troponin I or T Uric acid (Urate) Lipase Amylase Myoglobin	Blood Glucose Ketones Leukocytes pH Protein Myoglobin	PT or INR aPTT

Abbreviations: ALT = alanine aminotransferase; ANC = absolute neutrophil count; AST = aspartate aminotransferase; BUN = blood urea nitrogen; CA19-9 = cancer antigen 19-9; CEA = carcinoembryonic antigen; CK = creatine kinase; CRP = C-reactive protein; FSH = follicle-stimulating hormone; INR = International Normalized Ratio; LDH = lactate dehydrogenase; LH = luteinizing hormone; pH = hydrogen ion concentration; PT = prothrombin time; aPPT = activated partial thromboplastin time; RBC = red blood cell(s); WBC = white blood cell(s); HIV = Human Immuno deficiency Virus.

a Direct bilirubin bilirubin (*and indirect – only applicable for France*) will be measured at screening only if total bilirubin values are abnormal; the result will be used to calculate indirect bilirubin levels for the purposes of determining eligibility to participate in the study.

For laboratory tests covered by the NCI-CTCAE v4.03, laboratory data will be graded accordingly. For laboratory tests covered by the NCI-CTCAE v4.03, Grade 0 will be assigned for all non-missing values not graded as 1 or higher. Grade 5 will not be used.

Sponsor specifications for lab toxicity grading will be described in a specific document, separately from the statistical analysis plan. Corrected Calcium will be derived for analyses purposes, as described in these specifications.

Graded hematology, coagulation, urinalysis, and clinical chemistry test results will be summarized by worst grade on study treatment period as well as in shift tables from Baseline to worst grade on study treatment period. For shift tables, the number of patients with missing data at Baseline or on study treatment period will be displayed.

For laboratory parameters that are not gradable by NCI-CTCAE v4.03, shift tables of normal-abnormal will be provided for worst post-baseline value (both directions).

Grade 3 and 4 observations will be listed on an individual basis.

Possible Hy's Law (subjects with any elevated ALT or AST of  $>3xULN$ , ALP  $<2xULN$ , and associated with an increase in total bilirubin  $\geq 2xULN$ ) and drug-induced liver injury (DILI) cases (AE preferred term) will be summarized. Drug-induced liver injuries will be flagged using the SMQ "Drug related hepatic disorders" (narrow terms). Hy's Law and drug-induced liver injuries will be considered after the first study treatment administration.

Values outside laboratory normal ranges and Hy's law will be flagged in the individual data listings of laboratory data in appendix 16 of the ICH report.

Laboratory data analyses will be generated for the subgroup of subjects in Japan.

#### **15.4. VITAL SIGNS**

The number and percentage of patients with at least one clinically notable abnormality (see Appendix 4) will be tabulated by type of abnormality. Clinically notable abnormality will be also tabulated in an individual data listing.

In addition, blood pressure (systolic, diastolic and both combined) shift table based on NCI-CTCAE v4.03 grade for hypertension at baseline and worst post-baseline values will be produced:

- Systolic BP (SBP) only (mmHg):

- Grade 0: < 120
- Grade 1: 120-139
- Grade 2: 140-159
- Grade 3: ≥ 160
- No Grade 4 or 5
- Diastolic BP (DBP) only (mmHg):
  - Grade 0: < 80
  - Grade 1: 80-89
  - Grade 2: 90-99
  - Grade 3: ≥ 100
- Systolic and diastolic BP combined (mmHg). Maximum grade based on SBP and DBP values will be considered:
  - Grade 0: SBP < 120 and DBP < 80
  - Grade 1: SBP in 120-139 or DBP in 80-89
  - Grade 2: SBP in 140-159 or DBP in 90-99
  - Grade 3: SBP ≥ 160 or DBP ≥ 100
  - No Grade 4 or 5

Clinically notable values will be flagged in the individual data listings of vital signs in appendix 16 of the ICH report.

### 15.5. ECG

Automatic corrections for QTcF will be used, whenever available. Otherwise QTcF will be calculated as  $QT / (60/HR)^{1/3}$  (rounded to the nearest integer).

Values of QTcF will be classified as following:

QTc Categories (ms)
≤450
451-480
481-500
>500

Changes from baseline of QTcF will be classified as following:

QTc change from baseline(ms)
≤30
31-60
>60

The number and percentage of patients with at least one clinically notable ECG abnormalities (see Appendix 4) will be tabulated by type of abnormalities.

Patients with clinically notable QTcF values >500 ms and changes from baseline >60 ms will be listed including the corresponding notable values and abnormality findings.

### 15.6. MUGA/ECHOCARDIOGRAM

Left Ventricular Ejection Fraction (LVEF) abnormalities will be defined by grade according to NCI-CTCAE version 4.03. Patient will be considered as having a LVEF abnormality if the worst post-baseline value is grade 2, 3 or 4 according to the following classification (as defined in NCI-CTCAE version 4.03):

- Grade 0: Non-missing value below Grade 2
- Grade 2:  $40\% \leq \text{LVEF value} \leq 50\%$  or  $-20\% < \text{absolute change from baseline} \leq -10\%$
- Grade 3:  $20\% \leq \text{LVEF value} < 40\%$  or  $\text{absolute change from baseline} \leq -20\%$
- Grade 4: LVEF value < 20%.

The following summaries will be produced for LVEF:

- Incidence of worst post-baseline LVEF value with NCI-CTCAE version 4.03 grades.
- Shift tables using NCI-CTCAE version 4.03 grades to compare baseline to the worst post-baseline LVEF value with NCI-CTCAE version 4.03 grades.
- Time to LVEF abnormalities will be presented as KM plots if at least 10 patients with abnormality are observed. Patients with no LVEF abnormality will be censored at their last on-treatment LVEF examination date. Patients with no adequate post-baseline LVEF

assessment will be censored at their date of first study treatment administration. Two types of abnormalities will be considered:

- LVEF value < 50%;
- LVEF value < 50% and/or absolute change from baseline  $\leq$  -10% .

Different modalities to assess LVEF might be used for the same patient, change from baseline and shift table will be provided regardless of the modality.

Patients with abnormalities (grade 2 or above NCI-CTCAE version 4.03) will be tabulated in an individual listing.

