8.3.5.2. Technical Procedure and Parameters

- **Electrocardiogram**

An ECG will be recorded as described on the flowchart (please refer to the flow-chart corresponding to the current period: Main study or Study extension) using the internationally recognized 12-lead cardiograph. An institutional cardiograph will be used.

Prior to performing the 12-lead ECG, subjects should rest in the supine position for at least 5 minutes. The ECG measurement performed at the Screening Visit will be used to determine eligibility. The mean of the triplicate ECG measurements recorded pre-dose on Cycle 1 Day 1 will serve as the subject's Baseline value for all postdose comparisons. The ECG measurement at any time point should be used for AE grading and recommended dose modifications.

When an ECG is to be performed at the same time point as a blood collection, the ECG is to be performed first.

Interpretation of the tracing, Heart Rate (HR), QTcF interval (Fridericia's correction formula), PR and QRS complex should be made by a qualified physician and evaluated as normal or abnormal. All data should be documented in the e-CRF.

Clinically significant abnormalities present when the subject signed the Screening informed consent should be reported in the e-CRF. New or worsened clinically significant findings occurring after the informed consent must be recorded in the e-CRF.

- **Echocardiogram/Multi-gated Acquisition Scans**

Cardiac ejection fraction will be assessed by transthoracic ECHO or MUGA scans as described on the flowchart (please refer to the flow-chart corresponding to the current period: Main study or Study extension). The same method should be used throughout the study.

Subjects who develop signs/symptoms of congestive heart failure at any point during the study are required to have an evaluation of LVEF measurement by ECHO or MUGA.

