h	Electrocardiograms are to be performed in triplicate predose on Cycle 1 Day 1 (conducted within approximately 5 to 10 minutes total time), followed by a single ECG at 2.0 ( $\pm$ 0.5) hours after administration of encorafenib and binimetinib and before the start of the cetuximab infusion. Single ECGs are to be performed on Cycle 2 Day 1 predose and at 2.0 (+ 0.5) hours after administration of encorafenib and binimetinib and before the start of the cetuximab infusion. Single ECGs are to be performed predose at remaining time points. Electrocardiograms should be performed prior to PK and PD blood collection at equivalent nominal timepoints.
i	Visual assessment (General inspection of the eyes, examination of motility and alignment, visual disturbance including diminished central vision, blurred vision or loss of vision) to be performed on site by the investigator. Full ophthalmic examination by ophthalmologist to be performed at EOT and, if clinically indicated during treatment,, including best corrected visual acuity for distance testing, OCT and/or fluorescein angiography, slit lamp examination, intraocular pressure and dilated funduscopy with attention to retinal abnormalities. An ophthalmic examination at the 30-day follow up is only required if there was a clinically significant abnormality noted at EOT.
j	Dermatologic examinations are to be performed every 8 weeks from Cycle 1 Day 1 (i.e., on Day 1 of Cycles 3, 5, 7...).
k	ECHO/MUGA scans are to be performed on Cycle 2 Day 1 and Cycle 5 Day 1, then every 12 weeks and EOT
l	Tumor evaluations are to be performed every 6 weeks ( $\pm$ 7 days) from first dose for the first 12 weeks, then every 8 weeks ( $\pm$ 7 days) until disease progression. The time window allowed for the first tumor assessment (i.e. day 42 from first dose) is +7 days.
m	If a subject discontinue study treatment for reasons other than disease progression, then tumor assessments must be performed (as per local and central review) every 6 weeks (first 12 weeks) then every 8 weeks until the start of new anti-cancer therapy, disease progression, death, lost to follow-up, subject's decision or consent withdrawn.

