#### 9.4. BASELINE

*Baseline* is defined as the last available assessment before the first study treatment administration, unless otherwise specified.

If an assessment is planned to be performed prior to the first dose of study treatment in the protocol and the assessment is performed on the same day as the first administration of study drug, it will be assumed that it was performed prior to study treatment administration (if time is not available).

Unscheduled assessments will be used in the determination of baseline.

ECG Baseline will be the mean of the triplicate measurements at Cycle 1 Day 1 before the first study treatment administration.

Change from baseline will be defined as the difference between the value of the endpoint at the time point of interest and the baseline value.

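### SAP 15.6 pools ECHO and MUGA readings when it derives LVEF change from baseline, so a scan by a different method can create an apparent Grade 2 abnormality or mask a true fall

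*SAP*

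**What the plan says.** Protocol 8.3.5.2 permits two techniques ("Cardiac ejection fraction will be assessed by transthoracic ECHO or MUGA scans") and then instructs: "The same method should be used throughout the study". It gives no reason for the instruction.

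SAP 15.6 anticipates departures: "Different modalities to assess LVEF might be used for the same patient". For those patients, "change from baseline and shift table will be provided regardless of the modality".

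Four other SAP rules decide what this does to the results:

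- Classification in SAP 15.6: "Patient will be considered as having a LVEF abnormality if the worst post-baseline value is grade 2, 3 or 4". Grade 2 is reached by a value from 40 to 50%, or by an absolute change of -10 points or lower but above -20. Grade 3 is reached by a value from 20% to below 40%, or by a change of -20 points or lower.
- Time to abnormality in SAP 15.6: one Kaplan-Meier definition uses a value below 50% alone. The other uses "LVEF value < 50% and/or absolute change from baseline" of -10 points or lower.
- Baseline in SAP 9.4: it "is defined as the last available assessment before the first study treatment administration, unless otherwise specified". There is no condition on imaging method.
- Scan schedule in the SAP 6.9 flow-chart: "ECHO/MUGA scans are to be performed on Cycle 2 Day 1 and Cycle 5 Day 1, then every 12 weeks and EOT".

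The text of SAP 15.6 contains no same-method restriction, no count of patients who switched, no switch flag and no sensitivity analysis by method.

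**The concern.** A difference between an ECHO reading and a MUGA reading mixes any real change in the heart with the difference between the two techniques. The SAP's change criterion cannot separate them, and it does not need a low value as support: a patient who stays above 50% can still be graded on change alone.

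The sentence on modality names only change from baseline and the shift table. The incidence table, the Grade 2+ listing and the second Kaplan-Meier definition inherit the same treatment, because they rest on the same grades or the same change and no separate rule is given for them.

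Decreased ejection fraction is one of the clinically relevant binimetinib toxicities that Protocol 1.2.2 says should be monitored closely. Case numbers are likely to be small, so one or two misclassified patients would be visible. The Kaplan-Meier plots are produced only if at least 10 patients have an abnormality, so near that count a single case could decide whether a plot appears.

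**Working it through.** There is no stated figure to reproduce: no sample size, power or alpha depends on this rule. The check has two parts.

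**1. The SAP 15.6 rule applied to example readings.** Baseline and follow-up values are illustrative. Change = follow-up - baseline, in percentage points.

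| Baseline | Follow-up | Change | SAP grade |
|---|---|---|---|
| 65 | 60 | -5 | 0 |
| 60 | 51 | -9 | 0 |
| 65 | 55 | -10 | 2 |
| 70 | 60 | -10 | 2 |
| 75 | 55 | -20 | 3 |

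The last three rows are graded on change alone, since every follow-up value is above 50%. A pure method offset of 10 points would therefore be counted as Grade 2.

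Masking works the same way in reverse. A same-method fall from 65 to 54 is -11 points, Grade 2. If the second method read 3 points higher, the recorded value would be 54 + 3 = 57, the change 57 - 65 = -8, and the grade 0.

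**2. Chance of a false change when nothing has changed.** Model the recorded difference as normal with mean b (systematic offset) and standard deviation s. Then P(change ≤ c) = Φ((c - b)/s). Neither document gives b or s, so all values below are assumptions.

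| s | b | (-10 - b)/s | P(change ≤ -10) | (-20 - b)/s | P(change ≤ -20) |
|---|---|---|---|---|---|
| 6 | 0 | -1.67 | 4.8% | -3.33 | 0.04% |
| 7 | 0 | -1.43 | 7.7% | -2.86 | 0.2% |
| 6 | -3 | -1.17 | 12.2% | -2.83 | 0.2% |
| 7 | -3 | -1.00 | 15.9% | -2.43 | 0.8% |

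For comparison, an assumed same-method SD of 4 points with no offset gives (-10 - 0)/4 = -2.5, or 0.6%. If the between-method SD were 5 points with no offset, the figure would be 2.3%; at 3 points it would be 0.04%. The result depends strongly on the assumed spread.

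These are chances per switched comparison. A patient with several scans by the second method has several comparisons against the same baseline, and the worst one counts. The per-patient chance is then at least as high, but the comparisons are correlated, so no multiplied figure is given.

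**Scale in the trial.** If 2 to 10 patients each had one switched comparison (assumed), the expected number of false Grade 2 cases runs from 2 × 0.048 ≈ 0.1 to 10 × 0.159 ≈ 1.6.

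**The case against.** The strongest reply is that the SAP made an open, inclusive choice. It foresaw switches, said how they would be handled, and kept every scan, which is a defensible default for safety. Making the same-method analysis the main one would bring its own error: a true fall from 70 to 55 seen only on a switched scan is -15 points, yet it would become Grade 0 because 55 passes the absolute limits. That argument stands, and it determines which version should be main.

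Other mitigations also stand in part. The first Kaplan-Meier definition uses no baseline subtraction. Patients with Grade 2 or worse are listed individually. The detailed output specifications sit in an external file that is not available here, so a modality column may already be planned; only the SAP text can be judged. The protocol's instruction to keep one method suggests that switchers will be few.

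What the reply does not answer is comparability. Disclosing that methods are pooled does not make the pooled changes interpretable, and the SAP text offers no way to tell a method artefact from a fall.

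Several stronger readings are tempting but unsupported. A reader might infer that the protocol strictly requires one method because cross-method differences are not cardiac changes; it says should and gives no reason. A reader might infer that false Grade 3 cases are a material risk; on the assumptions above they stay below 1% per comparison. A reader might also infer that the SAP rule feeds into dose decisions. Protocol Table 14 is headed as recommended modifications, and its asymptomatic LVEF row needs both a fall of more than 10 points and a value below the institution's lower limit of normal. SAP 15.6 is a reporting rule only.

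**Conclusion.** The point holds as a minor improvement to a descriptive safety output. The SAP departs from the protocol's one-method instruction in how it computes change, and its change-only Grade 2 criterion, combined with the worst-value rule, lets one switched scan classify a patient in either direction.

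The size is about 5 to 8% per switched comparison for a false change of -10 points or more, or 12 to 16% with an offset of -3 points. This rests on assumed SDs of 6 to 7 points and a normal model. The number of patients affected is unknown and could be zero.

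It would be wrong to infer that the trial's efficacy conclusion is at risk. cORR and the two-stage test do not use LVEF, and SAP section 8 treats all results other than the primary test as exploratory.

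**What to change.** In SAP 15.6, keep the all-modality incidence, shift table and Kaplan-Meier analysis as the main, inclusive safety output. Then add:

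- a sensitivity version in which change-based grades and events use only scans by the baseline method, and switched scans are graded on the absolute LVEF limits alone;
- the number of patients whose method changed after baseline;
- the modality of each scan, and a flag for any switch, in the Grade 2+ listing.

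The cost is a few sentences in the SAP and one extra set of outputs. The sensitivity version can miss a true fall seen only on a switched scan, which is why it should sit beside the all-modality output and not replace it. If no patient switched, the count alone closes the question.

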### **15.7. ECOG PS**

ECOG PS will be summarized descriptively by time windows for each score category. Shift table to compare baseline to the worst post-baseline score will be produced.

### **15.8. PHYSICAL EXAMINATION**

The results on physical examination will not be tabulated as used to detect potential AE. They will be only listed in appendix 16 of the ICH report.

### **15.9. DERMATOLOGIC EXAMINATION**

Number of patients with post-Baseline skin abnormalities will be summarized by type of abnormalities (keratoacanthoma, squamous cell carcinoma, other).

### **15.10. OPHTHALMIC EXAMINATION**

All ophthalmic examinations will be listed:

- Visual assessment performed by the investigator: General inspection, Motility examination, Alignment examination, Visual disturbance
- Full ophthalmic examination: Tonometry, Visual acuity, Fundoscopy, Slit lamp, Optical Coherence Tomography (OCT), Fluorescein Angiography

General inspection, Motility examination, Alignment examination, Visual disturbance:

For each considered category, the number of subjects with at least one newly occurring abnormalities (whatever the clinical significance) will be described, on the subjects at risk of developing the abnormality. Subjects at risk of developing the abnormality will be defined as subjects with baseline not missing and not being abnormal (whatever the clinical significance) in both eyes, and with at least one post-baseline value).

Same analysis will be performed for the number of subjects with at least one newly occurring clinically significant abnormalities. Subjects at risk of developing the abnormality will be defined as subjects with baseline not missing and not being clinically significantly abnormal in both eyes, and with at least one post-baseline value).

Subjects with newly occurring abnormalities in general inspection, motility examination, alignment examination and visual disturbance respectively will be tabulated in a listing of individual data.

Visual acuity

Visual acuity will be measured using the Snellen visual acuity. This is determined by establishing the smallest optotypes that can be identified correctly by the patient at a given observation distance. Snellen visual acuity will be reported as a Snellen fraction (m/M) in which the numerator (m) indicates the test distance and the denominator (M) indicates the distance at which the gap of the equivalent Landolt ring subtends 1 minute of arc. For each timepoint, the LogMAR score will be calculated as  $-\log(m/M)$ . LogMAR is a notation of visual loss since positive logMAR values indicate reduced vision, while normal vision is indicated by negative logMAR numbers.

Total visual acuity score will also be assessed identifying clinically meaningful deterioration in visual acuity (LogMAR increase). LogMAR results will be summarized in a shift table from Baseline score ( $\leq 0$ ,  $>0$  to  $<0.1$ ,  $0.1$  to  $<0.2$ ,  $0.2$  to  $<0.3$  and  $\geq 0.3$ ) to worst post-baseline value ( $\leq 0$  (no deterioration),  $>0$  to  $<0.1$ ,  $0.1$  to  $<0.2$ ,  $0.2$  to  $<0.3$  and  $\geq 0.3$ ).

Ophthalmic events (AESI from groupings “Retinopathy excluding RVO” and “Retinal vein occlusion”) occurring within -15 days to 30 days of the worst logMAR score ( $\leq 0$ , 0 to  $<0.1$ , 0.1 to  $<0.2$ , 0.2 to  $<0.3$  or  $\geq 0.3$ ) will be presented by preferred term and worst logMAR score.

Patients with  $\geq 0.2$  LogMAR increase (visual loss) will be listed by patient and timepoint including the Snellen fraction and logMAR score.

All Snellen fraction and logMAR scores will be listed by eye in appendix 16 of the ICH report.

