17.4. SNELLEN EQUIVALENCE (VISUAL ACUITY CONVERSION CHART)

Line Number	Visual Angle (min)	Spatial Frequency (Cyc/deg)	LogMAR	Distance				Near					
				% Central Visual Efficiency	Snellen Equivalent			% Central Visual Efficiency	Inches (14/)	Centimeters (35/)	Revised Jaeger Standard	American Point-Type	"M" Notation
					Feet 20/	Meter 6/	Decimal						
-3	0.50	60.00	0.30	100	10	3.0	2.00	100	7.0	17.5	-	-	0.20
-2	0.63	48.00	0.20	100	12.5	3.8	1.60	100	8.8	21.9	-	-	0.25
-1	0.80	37.50	0.10	100	16	4.8	1.25	100	11.2	28.0	-	-	0.32
0	1.00	30.00	0.00	100	20	6.0	1.00	100	14.0	35.0	1	3	0.40
1	1.25	24.00	-0.10	95	25	7.5	0.80	100	17.5	43.8	2	4	0.50
-	1.50	20.00	-0.18	91	30	9.0	0.67	95	21.0	52.5	3	5	0.60
2	1.60	18.75	-0.20	90	32	9.6	0.63	94	22.4	56.0	4	6	0.64
3	2.00	15.00	-0.30	85	40	12.0	0.50	90	28.0	70.0	5	7	0.80
4	2.50	12.00	-0.40	75	50	15.0	0.40	50	35.0	87.5	6	8	1.0
-	3.00	10.00	-0.48	67	60	18.0	0.33	42	42.0	105.0	7	9	1.2
5	3.15	9.52	-0.50	65	63	18.9	0.32	40	44.1	110.3	8	10	1.3
-	3.50	8.57	-0.54	63	70	21.0	0.29	32	49.0	122.5	-	-	1.4
6	4.00	7.50	-0.60	60	80	24.0	0.25	20	56.0	140.0	9	11	1.6
7	5.00	6.00	-0.70	50	100	30.0	0.20	15	70.0	175.0	10	12	2.0
-	5.70	5.26	-0.76	44	114	34.2	0.18	12	79.8	199.5	11	13	2.3
8	6.25	4.80	-0.80	40	125	37.5	0.16	10	87.5	218.8	12	14	2.5
-	7.50	4.00	-0.88	32	150	45.0	0.13	6	105.0	262.5	-	-	3.0
9	8.00	3.75	-0.90	30	160	48.0	0.13	5	112.0	280.0	13	21	3.2
10	10.00	3.00	-1.00	20	200	60.0	0.10	2	140.0	350.0	14	23	4.0
11	12.50	2.40	-1.10	17	250	75.0	0.08	0	175.0	437.5	-	-	5.0
-	15.00	2.00	-1.18	16	300	90.0	0.07	0	210.0	525.0	-	-	6.0
12	16.00	1.88	-1.20	15	320	96.0	0.06	0	224.0	560.0	-	-	6.4
13	20.00	1.50	-1.30	10	400	120.0	0.05	0	280.0	700.0	-	-	8.0
16	40.00	0.75	-1.60	5	800	240.0	0.03	0	560.0	1400.0	-	-	16.0
20	100.00	0.30	-2.00	0	2000'	600.0	0.01	0	1400.0	3500.0	-	-	40.0
30	1000.00	0.03	-3.00	0	20000'	6000.0	0.001	0	14000.0	35000.0	-	-	400.0

Bold values are standard logMAR progression.
 LogMAR = logarithm of the minimum angle of resolution
 *20/2000 is equivalent to counting fingers @ 2 feet
 †20/20000 is equivalent to hand motion @ 2 feet

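### The visual acuity summary tables band absolute logMAR scores instead of change from baseline, so some real losses are labelled as no deterioration or show no shift

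*SAP*

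**What the plan says.** SAP 15.10 (Visual acuity) takes acuity as a Snellen fraction m/M. "For each timepoint, the LogMAR score will be calculated as" −log(m/M), with no log base stated. Its sign convention is that "positive logMAR values indicate reduced vision, while normal vision is indicated by negative logMAR numbers".

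The aim is given as "Total visual acuity score will also be assessed identifying clinically meaningful deterioration in visual acuity (LogMAR increase"), which is a change. Four outputs follow:

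- A shift table: "LogMAR results will be summarized in a shift table from Baseline score" "to worst post-baseline value". Both axes use the bands ≤0, >0 to <0.1, 0.1 to <0.2, 0.2 to <0.3 and ≥0.3. On the post-baseline axis the ≤0 band is annotated as no deterioration; no other band carries a label.
- A table of retinopathy and retinal vein occlusion events by preferred term and worst logMAR score, in essentially the same absolute bands. Its first two bands, ≤0 and 0 to <0.1, both contain 0.
- A listing for patients with at least a 0.2 rise: "LogMAR increase (visual loss) will be listed by patient and timepoint".
- A listing of all Snellen fractions and logMAR scores by eye.

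Protocol 17.4 gives a conversion chart whose footnote reads "LogMAR = logarithm of the minimum angle of resolution". The chart prints positive logMAR for vision better than 20/20 and negative logMAR for worse vision.

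**The concern.** The stated aim concerns change, but both summary tables classify by score. A score at or below 0 says that vision is 20/20 or better. It does not say that vision has not fallen. The SAP version history suggests how this arose: the first SAP version applied the same cut-points and the same annotation to the increase in score, and version 2 moved them to a baseline-by-worst table. That is background only; the point rests on the current text.

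Three consequences follow. A loss from better-than-normal vision down to 20/20 is annotated as none. A further loss in someone already at 20/40 or worse stays in one cell. And the event table ignores where the subject started.

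This matters because ophthalmic findings are a secondary safety endpoint (Protocol 2.5) and retinal events are a recognised binimetinib toxicity. Protocol Table 4 reports grade 1-2 retinal detachment in 39 of 269 patients (14%) on binimetinib alone, and Table 6 reports blurred vision in 8 of 30 on the triplet. During treatment a full ophthalmic examination is required only if clinically indicated, and then at end of treatment. Acuity data will be sparse, and each misplaced subject counts.

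**Working it through.** **Inputs.** The formula, sign, bands and 0.2 listing rule come from SAP 15.10. The chart values come from Protocol 17.4. I take base 10 because it reproduces the chart's magnitudes, and I round to two decimals as the chart does. SAP 15.10 states no rounding rule; the examples on which the conclusion rests do not depend on it.

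**Step 1: reproduce the printed logMAR values.** Apply −log10(20/M) to the 26 chart rows. All 26 agree in magnitude. The sign is opposite in the 25 non-zero rows; only 20/20 = 0.00 agrees. The chart's own definition, log10 of the visual angle, gives the SAP's sign: for 20/40 the angle is 2.00 and log10(2.00) = +0.30, against −0.30 printed.

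| Snellen | −log10(20/M) | Protocol 17.4 |
|---|---|---|
| 20/10 | −0.30 | +0.30 |
| 20/12.5 | −0.20 | +0.20 |
| 20/16 | −0.10 | +0.10 |
| 20/20 | 0.00 | 0.00 |
| 20/40 | 0.30 | −0.30 |
| 20/200 | 1.00 | −1.00 |

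**Step 2: place example subjects in the tables, using the SAP formula.** Change = worst − baseline.

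| Baseline to worst | Change | SAP cell | Band of the change | In the ≥0.2 listing |
|---|---|---|---|---|
| 20/10 to 20/20 | 0.00 − (−0.30) = +0.30 | ≤0 to ≤0, *no deterioration* | ≥0.3 | yes |
| 20/12.5 to 20/20 | 0.00 − (−0.20) = +0.20 | ≤0 to ≤0, *no deterioration* | 0.2 to <0.3 | yes |
| 20/16 to 20/20 | 0.00 − (−0.10) = +0.10 | ≤0 to ≤0, *no deterioration* | 0.1 to <0.2 | no |
| 20/20 to 20/40 | 0.30 − 0.00 = +0.30 | ≤0 to ≥0.3 | ≥0.3 | yes |
| 20/40 to 20/200 | 1.00 − 0.30 = +0.70 | ≥0.3 to ≥0.3 | ≥0.3 | yes |
| 20/40 unchanged | 0.30 − 0.30 = 0.00 | ≥0.3 to ≥0.3 | ≤0 | no |

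**Step 3: read the results.**

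- Rows 1 and 2 contradict the listing rule in the same section: they are listed as visual loss and tabulated as no deterioration. Row 3 is neither listed nor shown as a shift.
- Rows 5 and 6 share a cell, so the shift table cannot tell a 0.70 loss from stable vision. In the protocol's own grading of serous retinal detachment (Table 10), 20/40 is grade 2 acuity and 20/200 is grade 4; the open top band merges them.
- In the event table, row 6 appears in the worst band although nothing changed. Protocol Table 14 says that acuity impairment at screening counts as the subject's baseline.
- Row 4 shows the table working as intended when a loss crosses a band.

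**Step 4: bound the false label.** Under the SAP sign it requires a baseline better than 20/20 and a worst value of 20/20 or better. On the chart's range the largest such loss is 0.30 (20/10 to 20/20).

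**The case against.** The strongest reply is that nothing is hidden. Every rise of at least 0.2 is listed by timepoint, and every score is listed by eye, so the 20/12.5 and 20/200 examples would both be found. The shift table also displays any loss that crosses a band. A reader might infer that the tables cannot count subjects who lost vision; that goes too far, as the 20/20 to 20/40 case shows.

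Second, baseline-to-worst tables on absolute categories are this SAP's normal safety format (laboratory, blood pressure, ECOG), and an open top category is common. That is fair, but none of those tables describes a category as showing no deterioration. The left ventricular ejection fraction grades in SAP 15.6 include absolute change from baseline in their definition.

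Third, eye toxicity is also summarised through adverse events of special interest by grade, newly occurring visual disturbance, OCT and angiography, and fundoscopy and slit lamp. A retinal signal would not rest on these two tables. This stands, and it limits the stakes.

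Fourth, the event table only cross-tabulates terms with scores and makes no causal claim. That is also true. Without a baseline reference, though, it still cannot show whether an event was accompanied by loss.

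What remains is that listings give no counts, and the only two summaries of acuity do not measure what the section says it is looking for.

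**Conclusion.** The point holds for the two summary tables. They classify by score, while the aim and the listing rule concern change. One annotation is wrong for any subject whose baseline is better than 20/20 and who falls but stays at 20/20 or better. The open top band conceals further loss from 20/40 or worse, and the event table cannot separate pre-existing from new impairment. The number of subjects affected depends on the baseline acuity distribution, which neither document gives; if no baseline is better than 20/20, the false label never arises. The effect is on descriptive safety reporting only, because SAP section 8 reserves causal interpretation for the primary test.

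Two stronger readings are not supported. A reader might infer that the reversed chart turns the results upside down. With chart values, 20/200 (−1.00) would indeed fall in the ≤0 band and the listing of increases would work backwards. But SAP 15.10 computes logMAR from the Snellen fraction with its own sign and does not refer to Protocol 17.4, so the chart affects results only if someone substitutes its values. A reader might also infer that a natural log will be used, giving −ln(20/25) = 0.22 instead of 0.10. The cut-points and the chart's magnitudes both indicate base 10. Both matters are clarifications, not evidence of a wrong result.

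**What to change.** Replace the score shift table with a table of the worst per-eye change from baseline in logMAR: ≤0 (no deterioration), >0 to <0.1, 0.1 to <0.2, 0.2 to <0.3, ≥0.3. Use the same change bands in the table of ophthalmic events; this also removes the overlap at 0. Take the worst eye there, unless the laterality of adverse events is collected, which the documents do not show. If the score shift table is kept alongside, drop its no-deterioration annotation. Dropping the annotation alone would leave the 20/40 to 20/200 gap open. Protocol 13.9.4 already provides for changes from baseline and/or shift tables, so this stays within the protocol.

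As secondary corrections, write the formula as −log10(m/M) and reconcile the sign of the logMAR column in Protocol 17.4 with SAP 15.10.

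The cost is a short SAP edit, two descriptive tables reprogrammed from acuity data already held by eye, and a sign correction in a protocol appendix. No new data are needed.
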